### 4.1 Inclusion and Exclusion Criteria

#### 4.1.1 Inclusion Criteria

- 101 Subject has provided informed consent prior to initiation of any study-specific activities/procedures.
- 102 Age  $\geq 18$  to  $\leq 85$  at the time of screening.
- 103 History of chronic stable angina for at least 3 months prior to screening, with at least 1 angina episode/month, on average over that period.
- 104 Ischemic heart disease documented by any one or more of the following:
- a. A history of myocardial infarction (MI) with elevated Creatine kinase - myocardial band (CK-MB), troponin I or T, or the presence of electrocardiogram (ECG) changes consistent with an MI, or
  - b. Coronary angiography demonstrating at least 1 major epicardial coronary artery (eg, left anterior descending, left circumflex, or right coronary artery) with a stenosis of at least 50% diameter or greater but excluding  $> 50\%$  or flow-limiting stenosis of the left main coronary artery unless revascularized by coronary artery bypass grafting, or
  - c. Revascularization procedure (eg, cardiac bypass graft, angioplasty)  $\geq 3$  months prior to screening

Product: Erenumab (AMG 334)  
Protocol Number: 20140254  
Date: 28 October 2016

Page 18 of 63

- 105 Receiving stable doses of cardiac medications (eg, beta blockers, calcium channel blockers, antianginals, etc.) for at least 30 days prior to randomization and that are not expected to change during the study
- 106 Completes 2 qualifying ETTs during screening period (as described for Screening in [Section 7.3.7](#) and [Section 7.3.8](#)). The following ETT qualifications are required:
- a. Limitation of exercise due to symptoms related to myocardial ischemia (such as angina pectoris, chest pain/discomfort, dyspnea, shortness of breath), or  $\geq 3$  mm ST-segment depression
  - b.  $\geq 1.0$  mm ischemic ST-segment depression during exercise performance
  - c. Exercise duration of  $\geq 3$  to  $\leq 12$  minutes, and
  - d.  $\leq 1$  minute difference or within 20% duration (using the longest duration qualifying ETT) in TET between the 2 qualifying ETTs
  - e. ECG tracings from screening ETTs are acceptable to the core ECG laboratory

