### Measurement

The measurement of ST-segment depression during exercise should be based on the average of at least 3 consecutive ST-segments. Any computer-generated determination of ST-segment depression should be verified by review of the ECGs to confirm that they meet criteria for ischemic ST-segment depression. ST-segment deviation should be visually monitored throughout the ETT. Frequent 12-lead ECGs (ie, every 30 seconds) must be recorded until resolution of the ST-segment depression.

The ECG tracings are to be properly labeled, with one copy maintained in the subject's source records and one copy provided to the core ECG laboratory, per the instructions provided in the ETT Manual. Analysis of the ETT parameters will be performed by the core ECG laboratory.

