3.2 Sample Size

The primary endpoint is the change from baseline in TET. Assuming between-subject standard deviation for change from baseline in exercise duration of 130 seconds, with a planned study size of at least 27 subjects in each group and a difference in change from baseline in exercise duration of 0 seconds between AMG 334 group and placebo group, there is an 80% probability (power) that the lower bound of the 90% confidence interval

(CI) will exceed -90 seconds. A margin larger than -60 seconds between groups was required to accommodate the possibility of more than 60 second (up to 20%) difference allowed in qualifying TETs for individual subjects. Because of this within-subject TET variation, a maximum TET difference of 90 seconds between the AMG 334 group and placebo group was considered reasonable in this study. A margin of -90 seconds was selected, which corresponds to the margin used in previous study testing a comparable hypothesis (Patterson, et.al 2005). Twenty-nine subjects are needed in each group if considering 5% dropout.

When approximately 45 subjects have been enrolled, Amgen may conduct a blinded sample size-estimation and may choose to alter the sample size based on the blinded variance in the pooled treatment groups.

4. Study Endpoints and Covariates

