10.5.2 Analyses of Secondary Efficacy Endpoints

The secondary endpoints are time to onset of exercise-induced angina and time to onset of ≥ 1 mm ST-segment depression.

For time-to-event endpoints, only the first occurrence will be considered. If no event is observed during ETTr, then this subject will be considered as censored at the end of ETTr.

Kaplan-Meier estimates of the event-free time to ST-segment depression and exercise induced angina will be computed and graphically displayed using the EAS. For each endpoint, a stratified (< 7 or ≥ 7 minute randomization strata) log-rank test statistic will be calculated to compare the two treatment groups at a significance level of 0.10.

As a secondary analysis, the hazard ratio and its 90% CI for AMG 334 vs placebo will be estimated using a stratified (< 7 or ≥ 7 minute randomization strata) Cox proportional hazards regression model. The proportional hazards assumption will be assessed by visual inspection for parallel lines over time in the plot of log-negative-log of the survival function vs. log (time) (Hosmer and Lemeshow, 1999). If there is strong evidence of non-proportional hazards for the treatment group, then a piece-wise Cox model (Collett, 2003) or an accelerated failure time (AFT) model will be considered. Regardless of non-proportionality, the main analysis of the primary endpoint will be in terms of the Cox model.

Summary statistics (mean, median, Q1, Q3, and 90% CI) of time to event will be provided by treatment group. The number and percentage of subjects with an observed event will also be provided.

Sensitivity analyses described below will be performed for the secondary endpoints:

- Repeat the secondary analysis (Cox proportional hazards regression) using baseline TET as a continuous measure
- Repeat the primary and secondary analysis using PPS

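### No analysis of the onset endpoints uses the subject's own onset time from the qualifying treadmill tests; any power gain from doing so depends on reproducibility that the documents do not give

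*SAP*

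**What the plan says.** SAP 4.2 names one covariate for the primary analysis of the efficacy endpoints: baseline TET split at 7 minutes. SAP 6.3 defines a two-test baseline for TET and for no other treadmill variable.

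For both onset endpoints, SAP Table 1 and SAP 10.5.2 make the log-rank test, stratified by TET at 7 minutes and tested at 0.10, the primary analysis. The two places differ on the Cox model. Table 1 lists continuous baseline TET as the secondary analysis. Section 10.5.2 makes the TET-stratified Cox model secondary and gives continuous TET as a sensitivity analysis: "Repeat the secondary analysis (Cox proportional hazards regression) using baseline TET as a continuous measure". Under either reading, TET is the only baseline information used.

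The screening tests should already contain the more direct baseline. Criterion 106b in Protocol 4.1.1 requires at least 1.0 mm "ischemic ST-segment depression during exercise performance" in the qualifying tests, and 106e requires tracings acceptable to the core laboratory. Protocol 7.3.9.3 (Measurement) adds: "Analysis of the ETT parameters will be performed by the core ECG laboratory". That sentence is not limited to the post-dose test (ETTr).

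**The concern.** Subjects differ widely in how soon ischaemia appears on a treadmill, and that spread is noise in a comparison of onset times. A subject's own onset time in two recent tests is a natural predictor of onset in the ETTr. The plan instead uses TET, which measures when the subject stopped.

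This is a safety question. The onset tests look for earlier ischaemia on drug, and a non-significant result may be read as reassuring. The plan states no power for them and the trial is small, so precision from data already collected is worth having.

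**Working it through.** **1. The plan's own figure.** Inputs from SAP 3.2: "Assuming between-subject standard deviation for change from baseline in exercise duration of 130 seconds"; "planned study size of at least 27 subjects in each group"; "A margin of -90 seconds was selected"; true difference 0; one-sided 0.05 (the 90% interval).

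n per arm = 2 × 130² × (1.645 + 0.842)² / 90² ≈ 25.8, so 26 by the normal approximation. With the t distribution, power is 79.3% at 26 and 80.7% at 27. Dropout: 27 / 0.95 = 28.4, so 29, matching "Twenty-nine subjects are needed in each group if considering 5% dropout". The stated design reproduces. It concerns the primary endpoint only.

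**2. What the planned log-rank test can detect** (1:1 allocation, two-sided 0.10). The hazard ratio for 80% power is exp{√[4 × (1.645 + 0.842)² / events]}.

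- 54 events: 1.97
- 43 events: 2.14
- 27 events: 2.60

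At a hazard ratio of 1.5, power is 44% with 54 events and 38% with 43. The documents give no event count; 54 is everyone and 43 is about 80%.

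**3. What the baseline onset time would add.** Simulation of 27 per arm, 1,500 trials per setting, with critical values from null simulations so that each test has true size 10%. Assumed, not in the documents: SD of log onset 0.30, 15% shorter onset on drug, 20% censored, and TET itself highly reproducible (ICC 0.85), which favours the TET comparator. Time runs from the start of the ETTr. Ranges are over an onset–TET correlation of 0.5 to 0.9.

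| Single-test ICC of onset | Stratified log-rank | Stratified Cox + baseline onset | Gain over log-rank (points) | Gain over Cox with continuous TET (points) |
|---|---|---|---|---|
| 0.3 | 55–58% | 56–58% | about 0 | −2 to 0 |
| 0.5 | 56–62% | 64–67% | 5 to 9 | 2 to 9 |
| 0.6 | 55–64% | 68–72% | 8 to 13 | 2.5 to 11 |
| 0.7 | 56–68% | 76–79% | 11 to 20 | 4 to 17 |
| 0.85 | 57–71% | 93–94% | 23 to 36 | 12 to 36 |

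A second simulation (54 subjects, 45–49 events, 15% shorter onset) gave gains over the log-rank test of 0–1 points at ICC 0.3, 9–14 at 0.5 and 17–22 at 0.7. Across both, the gain is about 0–14 points at ICC 0.3–0.6 and 11–36 at 0.7–0.85.

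**4. Where the ICC might lie.** The only guide is the 130 s SD. For a change from a two-test mean, the variance is 1.5 × the within-test variance, so the within-test SD of TET is √(130² / 1.5) ≈ 106 s. If the SD of baseline TET is 110, 130 or 156 s (assumed), the between-subject variance is SD² − 106²/2 and the ICC is 0.36, 0.50 or 0.62. If onset times behave like TET, the lower rows of gain apply, roughly 0–13 points in the tabulated simulation.

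**5. The clock.** SAP 6.4 measures time from receipt of investigational product. At ICC 0.7 and onset–TET correlation 0.7, the log-rank and onset-adjusted powers are 60% and 77% from the start of the ETTr. From receipt of product they are 43% and 52% if the infusion-to-test gap has SD 1 minute, 14% and 15% at 5 minutes, and 11% and 11% at 10 minutes (gap SDs assumed).

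**6. Size of the adjusted test.** With asymptotic critical values and no drug effect, the onset-adjusted Cox test rejected in about 11–15% of trials at nominal 10%. The log-rank test rejected in about 10–11%.

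**The case against.** The strongest reply is that the size of the gain rests on assumption. SAP 3.2 powers only the primary endpoint, and the documents give no SD, test–retest correlation or event count for onset time. This stands. Criteria 106d (agreement in TET) and 216d (exclusion of unstable ST response) may select reproducible subjects, but no figure follows from them.

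Second, the SAP already plans a Cox model with continuous TET, and in subjects whose exercise is limited by ischaemia TET may track onset closely. This also stands: at an onset–TET correlation of 0.9 and ICC 0.7, the gain over that model is only 4 points.

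Third, under the SAP 6.4 clock the covariate could achieve almost nothing. This stands and sets the order of the changes.

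Fourth, baseline angina onset may be missing, because 106a also admits subjects limited by dyspnoea or by ≥ 3 mm ST depression. The evidence here is for ST depression only.

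Fifth, baseline ST onset may be coarse: Protocol 7.3.9.2 takes ECGs every minute, then every 30 seconds once ST changes occur. That would lower the ICC and is part of the uncertainty.

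A reader might also see a contradiction in a primary endpoint defined as change from baseline beside secondary endpoints that are not. There is none: Protocol 10.1.1.2 defines the latter as onset times during the test. The issue is efficiency.

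**Conclusion.** The omission is real. The onset analyses use only TET, although a baseline time to ≥ 1 mm ST depression should exist for every eligible subject. Adjusting for it is a sound, optional improvement: calibrated power showed no material loss and a gain over the planned log-rank test of about 0–14 points at ICC 0.3–0.6 and 11–36 at 0.7–0.85, generally less against Cox with continuous TET. These figures rest on the assumed onset spread, effect, censoring and reproducibility, and on a clock that starts with the ETTr.

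A reader might infer that the plan gives up substantial power on both secondary endpoints. The documents do not support that. They give no reproducibility for onset time; the plan's own SD, read across to onset, is compatible with a gain near zero; and nothing has been shown for angina.

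**What to change.** 1. Reconcile SAP 6.4 with the endpoint as listed (SAP 4.1.2, Protocol 10.1.1.2), so that time runs from the start of the ETTr. Without this, the remaining steps have little value.
2. In SAP 6.3, define baseline time to ≥ 1 mm ST depression as the mean over the two qualifying tests.
3. In Table 1 and 10.5.2, specify one Cox model for the ST endpoint, stratified by the randomisation strata with log mean baseline onset time as covariate. This also removes the present disagreement between those two places.
4. Name the governing analysis. Either the adjusted Cox model governs, in which case SAP 11 must record the departure from the log-rank test in Protocol 10.5.4, or the unadjusted stratified log-rank test still governs and the Cox model is the prespecified adjusted estimate. In the second case the governing test gains no power.
5. Take the Cox p value by re-randomisation within strata, because the asymptotic test runs above its nominal size.
6. For angina, apply the covariate only with a prespecified rule for subjects without baseline angina onset; otherwise leave that analysis as planned.

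Cost: a line in the data-transfer plan so that the core laboratory's screening onset times reach the analysis data, one derivation, and a re-randomisation program. No subjects or procedures are added. The wording must be final before unblinding. If the sponsor prefers not to adjust, a sentence justifying the omission would do.

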10.6 Safety Analyses

10.6.1 Adverse Events

The Medical Dictionary for Regulatory Activities (MedDRA) version 18.0 or later will be used to code all events categorized as AEs and Disease-related Events (DREs) to a system organ class and a preferred term.

Subject incidence of AEs will be summarized for all treatment-emergent AEs, serious AEs, AEs leading to withdrawal of IP and fatal AEs. Subject incidence of all treatment-emergent AEs, serious AEs, AEs leading to withdrawal of IP and fatal AEs, will be tabulated by system organ class and preferred term in descending order of frequency. Subgroups group analyses (if there is a medical rationale) will be presented by system organ class and preferred term in descending order of frequency. All races (if appropriate) with less than 5% of the total enrolled subjects will be pooled together for summary purposes.

Subject-level data may be provided instead of tables if the subject incidence is low.

Subject incidence of DREs will be summarized for all treatment-emergent DREs and fatal DREs.

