## **9. SAFETY DATA COLLECTION, RECORDING, AND REPORTING**

### **9.1 Definition of Safety Events**

#### **9.1.1 Disease Related Events**

Disease Related Events are events (serious or non-serious) anticipated to occur in the study population due to the underlying disease. Such events do not meet the definition of an adverse event unless assessed to be more severe than expected for the subject's baseline condition. Disease-related events for the purposes of this study include angina pectoris and related symptoms such as chest pain and shortness of breath (refer to

---

CONFIDENTIAL

**AMGEN**®

---

**AMGEN**®

---

Product: Erenumab (AMG 334)  
Protocol Number: 20140254  
Date: 28 October 2016

Page 38 of 63

---

[Section 7.3.10](#)). Angina pectoris and related symptoms do not meet the definition of an adverse event unless assessed to be more severe than expected relative to the subject's baseline condition (refer to [Section 9.1.3](#)).

Disease Related Events and/or Disease Related Outcomes that do not qualify as Serious Adverse Events:

- An event which is part of the normal course of disease under study (eg, disease progression in oncology or hospitalization due to disease progression) is to be reported as a Disease Related Event.
- Death due to the disease under study is to be recorded on the Event CRF.

If the outcome of the underlying disease is worse than that which would normally be expected for the subject, or if the investigator believes there is a causal relationship between the investigational products/study treatment protocol required therapies and disease worsening, this must be reported as an adverse event or serious adverse event.

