### 9.1.3 Serious Adverse Events

A serious adverse event is defined as an adverse event that meets at least 1 of the following serious criteria (unless it meets the definition of a Disease Related Events as defined in [Section 9.1.1](#)):

- fatal
- life threatening (places the subject at immediate risk of death)
- requires in-patient hospitalization or prolongation of existing hospitalization
- results in persistent or significant disability/incapacity
- congenital anomaly/birth defect
- other medically important serious event

A disease related event is to be reported as a serious adverse event if:

the subject's pre-existing condition becomes worse than what the investigator would consider typical for a patient with the same underlying condition, or

if the investigator believes a causal relationship exists between the investigational medicinal product(s)/protocol-required therapies and the event,

and the event meets at least 1 of the serious criteria above

An adverse event would meet the criterion of "requires hospitalization", if the event necessitated an admission to a health care facility (eg, overnight stay).

If an investigator considers an event to be clinically important, but it does not meet any of the serious criteria, the event could be classified as a serious adverse event under the criterion of "other medically important serious event". Examples of such events could include allergic bronchospasm, convulsions, blood dyscrasias, drug induced liver injury ([DILI] see [Appendix A](#) for drug-induced liver injury reporting criteria), or events that necessitate an emergency room visit, outpatient surgery, or urgent intervention.

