6.5 Safety Endpoints

Treatment-Emergent Adverse Event

Events categorized as adverse events (AEs) starting on or after first dose of IP as determined by the flag indicating if the AEs started prior to the first dose on the Events CRF and up to and including 84 days after the end of IP or end of study, whichever comes first.

Serious adverse events (SAEs) are events categorized as AEs that are starting on or after first dose of IP as determined by the flag indicating if the adverse event started prior to the first dose of the Events CRF and up to and including 84 days after the end of investigational product.

Treatment-emergent Disease-related Event

Events categorized as Disease-related Events (DREs) starting on or after first dose of investigational product as determined by the flag indicated if the event started prior to the first dose on the Events CRF and up to and including 84 days after the end of investigational product.

Serious disease-related events are events are events categorized as DREs that are starting on or after first dose of investigational product as determined by the flag indicating if the event started prior to the first dose on the Events CRF and up to and including 84 days after the end of investigational product

Maximum Change from Baseline in SBP

The maximum change from baseline in SBP is calculated by the maximum value of (SBP after first dose date— baseline SBP)

Maximum Change from Baseline in HR

The maximum change from baseline in HR is calculated by the maximum value of (HR after first dose date – baseline HR)

Maximum Change from Baseline in ST-Segment Depression

The maximum change from baseline in ST-Segment Depression is calculated by the maximum value of (ST-Segment Depression after first dose— baseline ST-Segment Depression).

Columbia-Suicide Severity Rating Scale (C-SSRS)

The C-SSRS is a clinician rating of suicidal behavior and ideation. Two versions depending on the type of visits will be used in this study: Screening and Since Last Visit. The C-SSRS consists of a maximum of 20 items to evaluate suicidal behavior and suicidal ideation.

7. Analysis Subsets

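### Serious disease-related events are defined in the SAP but never summarised, so non-fatal serious angina that the investigator keeps as a disease-related event is not shown as serious by treatment group

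*SAP*

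**What the plan says.** Protocol 9.1.1 sets up the category: "Disease Related Events are events (serious or non-serious) anticipated to occur in the study population due to the underlying disease". It names angina, chest pain and breathlessness as DREs for this study. Among events to be reported as DREs it gives, as a generic example, a hospital stay caused by progression of the disease under study.

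Protocol 9.1.3 then defines an SAE as an adverse event meeting at least one serious criterion, "unless it meets the definition of a Disease Related Events". A DRE that meets a serious criterion becomes an SAE by either of two routes: the investigator considers the condition worse than typical, or believes the event was caused by the product or protocol-required therapy.

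SAP 6.5 keeps the two streams apart. On one side, "Serious adverse events (SAEs) are events categorized as AEs"; on the other, "Serious disease-related events are events are events categorized as DREs", with a time window.

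SAP 10.6.1 lists the outputs. For adverse events: "Subject incidence of AEs will be summarized for all treatment-emergent AEs, serious AEs, AEs leading to withdrawal of IP and fatal AEs". For DREs: "Subject incidence of DREs will be summarized for all treatment-emergent DREs and fatal DREs". Protocol 10.5.5 likewise plans tables of DREs and of fatal DREs, by system organ class and preferred term.

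**The concern.** The SAP defines a category and then gives it no output. Adverse events get a serious-event summary and DREs do not, so a serious, non-fatal DRE falls between the SAE table and the fatal-DRE table.

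This matters more here than in most trials. Protocol 2.2 raises the possibility that CGRP blockade interferes with protective mechanisms during ischaemia. Protocol 2.5 says the study should support safe use in people with, or at risk of, cardiovascular disease. DREs are a named safety endpoint beside adverse events (protocol 10.1.1.3, SAP 4.1.3). A reader of the study report would look to the serious-event tables for serious ischaemic symptoms by arm, and what those tables show would depend partly on an investigator's call about what is expected and unrelated.

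**Working it through.** The plan gives no figure on this point, so the main check traces one kind of event through the definitions to the tables. The event is a non-fatal angina episode after dosing that meets a serious criterion, such as hospital admission.

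| Investigator's view | Category (protocol 9.1.1, 9.1.3) | Where it is summarised (SAP 10.6.1, protocol 10.5.5) | Shown as serious? |
|---|---|---|---|
| Worse than typical | SAE | Serious AE tables | Yes |
| Related to product or protocol-required therapy | SAE | Serious AE tables | Yes |
| Expected and unrelated | Serious DRE | All-DRE summary only | No |

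Only the last row is a gap. Three other provisions might fill it:

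- Adjudication: protocol 7.3.11 sends cardiovascular events to a blinded independent committee, and SAP 9.2 names adjudicated events as a data source. SAP section 10 specifies no table of them.
- Data monitoring committee: protocol 9.2.2.4 and 10.5.2 and SAP section 8 describe review during the study. They specify no by-arm summary for the report.
- Subject-level data: SAP 10.6.1 permits these in place of tables when incidence is low. This is optional, and there is no planned serious-DRE table to replace.

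**Does the all-DRE summary separate these subjects?** Inclusion 103 requires at least one angina episode a month on average, and protocol 9.2.1 asks for all DREs over 12 weeks to be reported. Assume a Poisson rate of 1 a month and 84/30.4 = 2.76 months of follow-up. The share of subjects with at least one recorded DRE is 1 − exp(−2.76 × r), where r is the fraction of episodes recorded as DREs (not known):

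- r = 1: 1 − exp(−2.76) = 94%
- r = 0.5: 1 − exp(−1.38) = 75%
- r = 0.1: 1 − exp(−0.276) = 24%

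Unless recording is sparse, a subject admitted with angina sits among many subjects counted for minor episodes.

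**How many subjects might be affected?** No rate is given. For an assumed 12-week incidence p among 54 subjects, the expected number is 54p and the chance of at least one is 1 − (1 − p)^54:

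- p = 1%: 0.54 subjects; 1 − 0.99^54 = 42%
- p = 5%: 2.7 subjects; 1 − 0.95^54 = 94%
- p = 10%: 5.4 subjects; 1 − 0.90^54 = 99.7%

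**How far can classification move the table?** As a hypothetical case, suppose 3 of 27 subjects on drug and 0 of 27 on placebo have serious non-fatal angina, and j of the 3 are kept as DREs. The SAE table shows 3 − j against 0, anywhere from 3 against 0 to 0 against 0. A combined SAE-or-serious-DRE summary shows 3 against 0 for every j. Even that is not decisive: the two-sided Fisher p-value is 2 × C(27,3)/C(54,3) = 2 × 2925/24804 = 0.24.

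**Can the category be programmed?** The SAP 6.5 sentence reads "Serious disease-related events are events are events categorized as DREs that are starting on or after first dose of investigational product" and continues with the end of the window. It states when the event starts, but not what makes it serious.

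**The case against.** A reader might infer that hospitalised angina is missing from the serious-event comparison altogether. The documents do not support that. Serious angina judged worse than typical or related is an SAE, and protocol 9.2.2.4 expressly allows for an SAE of stable angina. Nor are events kept as DREs hidden: they are counted by arm, and what they lack is a seriousness flag.

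A reader might also infer that serious ischaemic events in general drop out. The DREs named are angina and related symptoms. The list is not closed, but infarction and stroke are not on it, and nothing shows them routinely leaving the SAE tables.

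The residual group may also be small. Subjects have stable angina, exclusion 216 removes recent unstable angina or acute coronary syndrome, and nothing says a subject's usual pattern includes admission. The hospitalisation example in protocol 9.1.1 uses oncology wording. Classification is made blind, since protocol 10.3 keeps site staff blinded until the final analysis, so there is no evident mechanism for bias between arms. Ischaemia is also compared directly through exercise time, time to angina and time to ST-segment depression. Finally, the SAP follows the protocol here.

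All of this stands, and it limits the size of the point. It does not supply the missing summary. Blinded misclassification can still dilute a difference, and agreement between SAP 10.6.1 and protocol 10.5.5 means only that both leave out the category that SAP 6.5 defines.

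**Conclusion.** The point holds for one group: non-fatal serious DREs that the investigator judges both expected and unrelated. These are never shown as serious by arm, and the serious-event comparison depends on that judgement. This is a reporting gap that is cheap to close. It is not an error in a planned test, and it touches no hypothesis, margin or decision rule.

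Its size cannot be fixed from the documents. Under the assumed 1% to 10% incidence it concerns roughly 0.5 to 5.4 of 54 subjects, so the added comparison would be descriptive only. The 3-against-0 case shows how classification acts on the table; it is not a prediction. The documents do not rank harms, so the importance given to serious angina here is an inference from the stated rationale.

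**What to change.** 1. In SAP 10.6.1, add subject incidence of serious treatment-emergent DREs by treatment group, system organ class and preferred term, or a listing by treatment group if there are few.
2. In SAP 10.6.1, add one combined summary by treatment group of subjects with any treatment-emergent SAE or serious DRE. This summary does not depend on whether the event was called expected or unrelated.
3. In SAP 6.5, state that a DRE is serious if it meets at least one of the serious criteria in protocol 9.1.3, within the window already given.
4. Confirm that the Event CRF records seriousness for DREs. The CRF is not among the documents, so this is an assumption until checked.

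The cost is two descriptive outputs, one clarified definition and the CRF check. How investigators classify or report events does not change, nor do sample size, error rate or power.
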